10.5	Reporting Urgent Safety Measures.....	18
10.6	Notification of Serious Breaches to GCP	18
11	Data management and quality assurance.....	18
11.1	Confidentiality.....	18
11.2	Data collection tools	18
11.3	Data handling and analysis	19
12	Record keeping and archiving	19
13	Statistical Considerations	19
13.1	Outcomes	19
13.1.1	Primary outcomes	19
13.1.2	Secondary outcomes.....	19
13.2	Sample size and recruitment	20
13.2.1	Sample size calculation	20
13.2.2	Planned recruitment rate.....	21
13.3	Statistical analysis plan	21
13.3.1	Primary outcome analysis.....	21
13.3.2	Secondary outcome analysis.....	21
13.3.3	Sensitivity and other planned analyses.....	21
13.4	Name of Committees involved in trial	21
14	Direct Access to Source Data/Documents	22
15	Ethics and regulatory requirements.....	22
16	Monitoring	22
17	Finance	22

18	Insurance.....	22
19	Statement of compliance	22

List of abbreviations

AE	Adverse Event
AR	Adverse Reaction
CA	Competent Authority
CI	Chief Investigator
CRF	Case Report Form
DMC	Data Monitoring Committee
DSUR	Development Safety Update Report
GCP	Good Clinical Practice
GOSH	Great Ormond Street Hospital
IB	Investigator Brochure
MHRA	Medicines and Healthcare products Regulatory Agency
PI	Principal Investigator
PIS	Participant Information Sheet
QA	Quality Assurance
QC	Quality Control
REC	Research Ethics Committee
SAR	Serious Adverse Reaction
SAE	Serious Adverse Event
SUSAR	Suspected Unexpected Serious Adverse Reaction
TMG	Trial Management Group
TSC	Trial Steering Committee

1 Trial personnel

Sponsor Representative:	[name] e-mail: [contact]
Chief investigator:	[name] e-mail: [contact]
Research Consultant:	[name] e-mail: [contact]
Lifebox clinical investigator:	[name] e-mail: [contact]
Research Associate:	[name] e-mail: [contact]
Consultant Medical Device Development:	[name] [contact]
Statistician:	[name] e-mail: [contact]

2 Summary

Objectives: The primary objective is to determine the proportion of oxygen saturation measurements obtained within 60 seconds when the oxygen saturation is measured by expert users and by trained healthcare workers using the redesigned Lifebox oximeter and probe for children aged 0-59 months

The secondary objective is to provide further description of the 'usability' of the redesigned oximeter and probe in children aged 0-59 months by healthcare workers, to assess how well children tolerate the probe, and the difference in time to a stable oximetry reading for expert users and healthcare workers in different settings, or for different ages of children.

Type of study: Mixed methods observational usability testing

Study design and methods: This observational usability testing involves three types of data collection from three sites in the UK, Malawi and Bangladesh. This protocol relates specifically to the UK testing at Great Ormond Street Hospital.

Expert usability testing: the probe and oximeter will be used by an expert on 204 stable children (i.e. not physiologically unstable or admitted to a high-dependency or intensive care unit) of different ages and with varying illness states. Children will be purposefully recruited from inpatient wards to meet age criteria by a clinical researcher. Following consent, an oxygen saturation measurement will be done by the expert user. An independent observer will note the condition of the child, along with other key demographic, performance and clinical features and the time to successful measurement of oxygen saturation.

Healthcare provider usability testing: the probe and oximeter will be used by healthcare providers on healthy or mild systemically ill patients (i.e. with a normal oxygen saturation, i.e. >94%). Children will be purposefully recruited from inpatient wards to meet age requirements by a clinical researcher and pre-screened for their oxygen saturation. 17 healthcare workers will be assessed for their performance with the prototype probe. Each HCW will undertake an oxygen saturation measurement on 12 children (maximum 204 children at Great Ormond Street Hospital). An independent observer will note the condition of the child, along with other key demographic, performance and clinical features and time to successful measurement of oxygen saturation.

Usability Questionnaire: HCW will be asked to complete a usability questionnaire to collect quantitative and qualitative feedback about the oximeter and probe usability. The questionnaire will be completed following the usability testing by all the healthcare providers.

Study duration per participant:	Healthcare providers are the main study participants and will be involved in the study between 1 and 4 hours, with each healthcare provider taking 12 oxygen saturation measurements.
	Children will be involved in the study intermittently for up to 80 minutes. Children will be assessed for recruitment and consented prior to each measurement.
Estimated total study duration:	4 weeks
Planned study sites:	Great Ormond Street Hospital [single-site]
Total number of participants planned:	17 healthcare providers, and up to 408 children aged 0-59 months
Main inclusion/exclusion criteria:	The study will be conducted in the inpatient wards of Great Ormond Street Hospital, with recruited healthcare providers and children aged 0-59 months. Inclusion: 
- Children aged 0-59 months in an inpatient ward at Great Ormond Street Hospital- Healthcare provider working on an inpatient ward at Great Ormond Street Hospital Exclusions: 
- Children aged >59 months- Children in critical condition- Guardians lacking capacity to give informed consent for their child- Guardians unable to speak English
Statistical methodology and analysis:	We will calculate the proportion of readings that meet the target product profile requirement of 95% stable readings within 60 seconds. We will describe the time to stable reading, looking at the median time and inter-quartile range. We will compare these descriptive statistics between patient age groups, expert and healthcare provider participants, and with measurements from sites in Malawi and Bangladesh. We will describe differences between these sub-groups using t-tests. Qualitative questionnaire data will be analysed using an inductive thematic approach.

3 Introduction

3.1 Background

Pneumonia is the leading infectious cause of death in children under five and causes an estimated 935,000 deaths every year. Most deaths occur in sub-Saharan Africa and Southeast Asia. The outcomes for children with pneumonia can be improved through appropriate treatment and better case management using the WHO Integrated Community Case Management guidelines (ICCM) and Integrated Management of Childhood Illness (IMCI) guidelines.

Severe pneumonia is associated with hypoxemia, and peripheral oxygen saturation (SpO_2) of less than 90% is associated with increased mortality. The WHO guidelines use this measure to differentiate pneumonia where the child needs referral for oxygen therapy and parenteral antibiotic treatment, from basic treatment which can be managed safely in the community with oral antibiotics. Hypoxemia can be detected non-invasively with a pulse oximeter. Routine screening for hypoxemia provides an opportunity for improved case management, referral and treatment decision making, and has been shown to improve outcomes in children with pneumonia in developing countries. Despite being in widespread use in high-income settings, the uptake of pulse oximeters in low-income countries has been limited due to cost, durability and lack of systems to support this essential technology.

The Lifebox Foundation was formed in 2011 to improve access to pulse oximeters in developing countries following the inclusion of pulse oximetry in the 2009 WHO Guidelines for Safe Surgery. These oximeters, designed in collaboration and with end-users from developing countries in mind, have received good feedback from anaesthetists, paediatricians and healthcare workers in developing countries. However, there are some key areas for improvement that are required to make suitable for use in routine paediatric pneumonia care. This includes the need to improve the reusable oximeter probe for neonates and infants, to reduce the time taken to obtain a reading when the oximeter is used for repeated spot checks, and to improve the battery life and resilience to power fluctuations.

The problem of probe design in children is common to all regions and all users, both expert and non-expert. The solution in high-income settings is to use single-use disposable oximeter probes with an adhesive strip, costing \$10-15 each, making this approach not sustainable in resource-poor settings. A re-designed oximeter and paediatric probes, optimised for use in routine care at all levels of the healthcare system, is an important step to improving pneumonia diagnostics and care.

3.2 Preclinical data

In order to ensure that any re-designed oximeter and probe is fit for purpose, a process of Human-Centred Design has been used for the re-design. Human Centred Design is an iterative creative process to problem solving where end-user engagement is embedded into all stages of the product design. Crucially this approach will help to ensure that the end-product will be context appropriate and reflect the specific requirements of healthcare workers who will be using the oximeter. To date we have conducted focus group discussions (FGDs) with healthcare providers in Malawi and Bangladesh, and elicited feedback from a group of international experts in pulse oximetry about the re-designed paediatric probe and oximeter. This feedback has led to changes and modifications in the design of the probe, with two rounds of prototypes developed prior to the one being taken forward to usability testing.

3.3 Rationale

This project aims to design an upgraded pulse oximeter and re-usable probes specifically for children aged 0-59 months, suitable for use in all healthcare settings. A target product profile (TPP) produced through expert consultation by the Bill and Melinda Gates Foundation forms the baseline for the re-design. It specifies the required performance, functional, design and stakeholder needs, with a focus on the design of the interface between the probe and the patient (i.e. how the probe is attached to the child). In the formative work for this study, we have gone through a human centred iterative design process, engaging with end-users in developing countries and international experts, to produce a redesigned probe and oximeter. We are now undertaking final usability testing to ensure that the redesigned oximeter and probe meet the TPP in a range of children and in three different sites with different levels of training of healthcare workers (Great Ormond Street Hospital, district hospitals and community hospitals in Malawi and Bangladesh). This clinical investigation plan relates to the study proposed at Great Ormond Street Hospital only, but the results obtained will be pooled with results from other sites.

Hypothesis: the redesigned probe and oximeter will perform according to the target product profile of achieving 95% of measurements within 60 seconds.

Feedback from end-users to date has highlighted that measurements can take between 2-15 minutes in some settings, such as with agitated children in rural community healthcare settings in low-income countries. Therefore, achieving 95% of measurements within 60 seconds would constitute a significant improvement in paediatric pulse oximetry for use in a wide range of settings.

3.4 Assessment and management of risk

This study is categorised as: Type A = No higher than the risk of standard medical care.

Pulse oximetry is a non-invasive measurement that is routinely done in Great Ormond Street Hospital, by all levels of healthcare providers. It poses no risk to the patient, and all measurements taken during the study will be done by either experts or healthcare providers with a minimum required training.

4 Objectives

Primary:

The primary objective is to determine the proportion of oxygen saturation measurements obtained within 60 seconds when the oxygen saturation is measured by expert users and by trained healthcare workers using the redesigned Lifebox oximeter and probe for children aged 0-59 months

Secondary:

The secondary objective is to provide further description of the usability of the redesigned oximeter and probe in children aged 0-59 months by expert users and healthcare workers:

- Is this pulse oximeter probe easy to use by an expert and by healthcare providers?
- Does this oximeter provide a reliable reading when used by an expert and by healthcare providers?
- Is the probe well tolerated by the child?
- Is there a difference in the time taken to obtain a stable oximetry reading by the expert user compared to healthcare providers in different settings, or for different ages of children?

5 Study design

This is an observational usability study. 'Usability' is a broad concept defined by the international standard ISO 9241-11 as:

The extent to which a product can be used by specified users to achieve specified goals with effectiveness, efficiency and satisfaction in a specified context of use.

There is no specific statistical test for usability. We have defined usability in this study as a measure that is clinically relevant, that is, the proportion of oxygen saturation measurements obtained within 60 seconds by any level of healthcare worker. This measure is taken from the TPP and is the parameter by which the redesigned probe and oximeter will be deemed a success, that is, for a target of 95% of measurements to be obtained within 60 seconds.

Time taken to obtain a reading is only one dimension of usability so we will also be using a mixed questionnaire with quantitative and qualitative data for feedback from end-users based on use failure modes effect analysis (U/FMEA) - this data will be important if we find a low proportion of measurements meet the TPP, to understand the barriers to effective use. These data will be interpreted together to give a broader conclusion of usability, alongside our primary end-point. We will collect additional observational data on the number of repositions of the oximeter probe, the quality of the waveform (used to judge whether a measurement is stable) and condition of the child.

There will be two different types of usability clinical testing performed in this stage, assessing slightly different usability criteria, initially with expert users and then by healthcare providers with a range of training and experience. The primary analysis for the timed outcome of usability will be a pooled analysis from all the participating sites, stratified by expert user and healthcare provider. As the oximeter and probe should be appropriate for different settings, albeit with different levels of staff training, this will provide us an overall measure of usability.

Expert usability testing: the probe and oximeter will be assessed on a range of children, including different ages and with varying illness states (excluding those who are critically ill). Children will be purposefully recruited from inpatient wards at GOSH to meet age criteria by a clinical researcher. The attending guardian will be given study information and asked for informed consent. Following consent, the expert user will take an oxygen saturation measurement. An independent observer will note the condition of the child, along with other key demographic, performance and clinical features, and the time to successful reading.

The end point for a successful reading is defined as the time from when the probe is placed on the child to when the reading is stable (one full screen of a stable pulse waveform); the user says 'STOP' at this point. The time for the successful reading, and the total time taken to obtain a reading including the number of attempts to obtain the reading will be recorded.

Healthcare provider usability testing: the probe and oximeter will be assessed on healthy or mild systemically ill patients (with a normal oxygen saturation, i.e. >94%). Children will be purposefully recruited from inpatient wards at GOSH to meet age requirements by a clinical researcher, who will pre-test children to ensure that their oxygen saturation is above 94% at the point of recruitment. Healthcare providers will be purposefully recruited in each site to have a range of pulse oximeter

experiences and qualifications. Healthcare providers and attending guardians will be given study information and asked for informed consent.

Following consent, the healthcare provider will take an oxygen saturation measurement. An independent observer will note the condition of the child, along with other key demographic, performance and clinical features, and time to successful measurement.

The end point for a successful reading is defined as the time from when the probe is placed on the child to when the reading is stable (one full screen of a stable pulse waveform); the user says 'STOP' at this point. The time for the successful reading, and the total time taken to obtain a reading including the number of attempts to obtain the reading will be recorded.

Usability Questionnaire: A usability questionnaire, which will provide a subjective rating of a product's usability, will be used to gather quantitative and qualitative measures of the new probes usability from the healthcare providers. The questionnaire will be conducted following the usability testing.

6 Selection of Subjects

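### At GOSH, experts and health workers measure differently selected children, so the unadjusted secondary comparison of the two user types mixes user with case mix

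*Combined protocol and SAP*

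**What the plan says.** **Who is measured.** In the Summary, "the probe and oximeter will be used by an expert on 204 stable children", "of different ages and with varying illness states". Section 5 repeats this for the expert part: "the probe and oximeter will be assessed on a range of children, including different ages and with varying illness states". For health workers, section 5 says "the probe and oximeter will be assessed on healthy or mild systemically ill patients (with a normal oxygen saturation, i.e. >94"%, and recruitment is by a clinical researcher "who will pre-test children to ensure that their oxygen saturation is above 94% at the point of recruitment". Section 6.2 limits the saturation exclusion to the health-worker part. In both parts sections 6.1 and 6.2 require clinical stability and exclude critically unwell children.

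**What is compared.** Section 4 asks, as a secondary objective, whether time to a stable reading differs between experts and health workers, and section 13.1.2 lists that difference as a secondary outcome. Section 13.3.1 also compares the proportion of successful readings between the user types by χ² test. Section 13.3.2 and the Summary compare times by t-test. None of these names a covariate, stratum or restriction for the child's condition or saturation.

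**What is judged against 95%.** Section 5 defines usability as "the proportion of oxygen saturation measurements obtained within 60 seconds by any level of healthcare worker". It also says, as does section 13.2.1, that the primary analysis pools sites and stratifies by user type. Section 13.1.1 says that expert and health-worker results are pooled. The table in section 13.2.1 puts the two user rows and a combined row of 1,224 under the same primary heading.

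**The concern.** Age is balanced by design: each health worker takes three readings in each of four age groups, and the table plans equal numbers per age group. Illness and saturation are not balanced, because one user type gets a screened group and the other does not. If the child's state affects time to a stable waveform, an unadjusted test credits that effect to the user. The plan itself treats the child's state as relevant. Section 3.3 cites agitated children as an example of slow readings, section 8.4 ties its stopping rule to a cooperative child, and section 9 says that the software was changed to respond faster at low perfusion.

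What is at stake is the reading of a secondary comparison. Case mix could produce an apparent gap between users or hide a real one.

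The pooling question is separate but related. A figure combined over user types averages two case mixes, so it can fall on a different side of 95% from either user-specific figure.

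**Working it through.** **The plan's own figure.** Section 13.2.1 gives no calculation for the user contrast. Its 292 is for one proportion: n = Z²p(1−p)/e² with p = 0.95 and e = 0.025. With Z = 1.96, n = 3.8416 × 0.0475 / 0.000625 = 291.96, so 292 is reproduced. (The printed line substitutes 0.95 for Z, which would give 68.6. Only the printed substitution is wrong.)

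**Inputs from the documents.** 204 readings per user type at GOSH; 612 per user type over three sites; target 95%; 12 readings per health worker.

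**Assumed inputs.** The documents give no success rates by condition, so these are illustrations only. There is no true user effect, and success is 95% in children who meet the health-worker criteria. A share s of the expert children falls outside those criteria and has success rate q. Readings are independent.

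Expert rate = (1 − s) × 0.95 + s × q, and the health-worker rate is 0.95. The spurious gap is s × (q − 0.95). Rejection probability is for the two-sided 5% χ² test, by normal approximation.

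| q | s | Expert rate | Gap (points) | Rejects, 204 v 204 | Rejects, 612 v 612 |
|---|---|---|---|---|---|
| 0.80 | 5% | 0.9425 | −0.75 | 6% | 9% |
| 0.80 | 10% | 0.935 | −1.5 | 10% | 20% |
| 0.80 | 20% | 0.920 | −3.0 | 23% | 57% |
| 0.80 | 30% | 0.905 | −4.5 | 42% | 86% |
| 0.90 | 10% | 0.945 | −0.5 | 6% | 7% |
| 0.90 | 20% | 0.940 | −1.0 | 7% | 12% |
| 0.90 | 30% | 0.935 | −1.5 | 10% | 20% |
| 1.00 | 10% | 0.955 | +0.5 | 6% | 7% |
| 1.00 | 20% | 0.960 | +1.0 | 8% | 14% |
| 1.00 | 30% | 0.965 | +1.5 | 12% | 26% |

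The 612 column applies only if Malawi and Bangladesh select children in the same way, which this protocol does not show. It "relates to the study proposed at Great Ormond Street Hospital only, but the results obtained will be pooled with results from other sites".

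**Masking (also assumed).** Suppose that experts succeed in 97% and health workers in 93% of mildly ill children, and that 20% of expert children are sicker with 80% success. The expert rate is 0.8 × 0.97 + 0.2 × 0.80 = 0.936. A true 4-point advantage then shows as 0.6 points, and power at 612 v 612 falls from about 90% to 6%.

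**Effect on a figure pooled over user types.** With equal numbers, the shift is half the gap. At q = 0.80 and s = 20%, (0.92 + 0.95)/2 = 0.935, a shift of 1.5 points.

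**Precision of the contrast.** Half-width = 1.96 × √[0.0475 × (Dₑ/nₑ + Dₕ/nₕ)], where D is the design effect for experts (e) and health workers (h).

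- Independent readings (both D = 1): 4.2 points at 204 v 204; 2.4 at 612 v 612.
- Assumed intraclass correlation of 0.05 within health workers, Dₕ = 1 + 11 × 0.05 = 1.55: 4.8 and 2.8.
- The same correlation with one expert per site (assumed), Dₑ = 1 + 203 × 0.05 = 11.15: 10.7 and 6.2.

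**The case against.** The strongest reply is that little rests on this contrast. The only hypothesis is that 95% of readings come within 60 seconds, success is defined by that proportion, and section 13.3.1 calls its analyses descriptive. This stands, and it limits the weight of the point. It does not remove it: section 13.3.2 says that statistical differences will be looked for, and the contrast is a listed secondary outcome.

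Section 5 also says openly that the two parts are "assessing slightly different usability criteria". That justifies separate estimates, but not an unadjusted test between them.

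The groups may overlap heavily, since both consist of clinically stable children. In section 6 the only criterion that differs is saturation. No passage links a saturation of 94% or below to a slower reading, and the endpoint is a stable waveform rather than a saturation value. All of this stands, so the bias may be small.

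If there are few experts, clustering by expert may limit the contrast more than case mix does: 10.7 points of half-width in the one-expert illustration, against gaps of at most 4.5. Adjustment for case mix would not cure that. The rejection rates above assume independence and do not describe that scenario.

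On pooling, section 13.1.1 could be read, alongside section 3.3, as pooling over sites. That is possible, but its sentence names the two user types, and the combined row in the table supports the other reading.

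Three stronger inferences are tempting, and the documents do not support them:

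- **That the device verdict or the user-specific proportions are biased.** Each proportion describes its own stated group of children.
- **That experts are bound to look worse.** The sign depends on rates that the documents do not give.
- **That the data form has no usable scale for condition.** The protocol defines none, but section 11.2 says that the tools have been developed, and the form is not among these documents.

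**Conclusion.** The point holds, as a limit on a secondary comparison that is cheap to repair. The texts settle that the two user types measure differently selected children at GOSH and that the planned tests ignore this. They do not settle how much it matters. Under the assumed rates the spurious gap runs from half a point in either direction, which is negligible, to a 4.5-point expert deficit. The corresponding false-positive rates at GOSH run from about 6% to 42%, with independent readings.

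Section 13.1.1 does conflict with sections 5 and 13.2.1 on whether user types are pooled, and no passage says which figure must reach 95%. The illustrated split (health workers 95%, experts 92%, combined 93.5%) shows that the choice can matter. It does place health workers exactly on the threshold, so it is not a forecast.

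The saturation wording is an editorial inconsistency. Section 6.2 excludes a child at exactly 95%, while the Summary, section 5 and section 8.2 admit one.

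**What to change.** 1. **User comparison** (sections 13.3.1 and 13.3.2, and the statistical entry in the Summary). Adjust or stratify by the child condition that the observer already notes, by SpO2 where a value is already recorded, and by age group and site. Allow for repeated readings within each user. As an alternative, run a sensitivity analysis that restricts expert readings to children who meet the health-worker criteria on recorded data. Present the unadjusted contrast as descriptive only. State the number of experts, and note that with few of them user type cannot be fully separated from the individual expert.
2. **Primary figure** (section 13.1.1). Agree with sections 5 and 13.2.1: pooled over sites, stratified by user type. State which figure is judged against 95%, and align the definition in section 5 and the combined row of the table with it.
3. **Saturation cut-off.** Reconcile the Summary and sections 5, 6.2 and 8.2.

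**Cost.** Mostly wording, plus a check that the data form records condition on the same categories in both parts. No extra pre-test of expert children is required. Intervals widen modestly. If 10–30% of GOSH expert readings are set aside, 184 to 143 remain against 204, and the half-width goes from 4.2 to 1.96 × √[0.0475 × (1/184 + 1/204)] = 4.3 points, or to 4.7 with 143, assuming independent readings.
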